Studies from the 1980s and 1990s investigated a variety of compounds for local instillations into the bladder in attempts to decrease bacteriuria and prevent infections. One of the more promising solutions instilled was povidone-iodine. A single preoperative instillation of 1% povidone-iodine prior to prostatectomy in patients with indwelling catheters reduced the rate of post-operative bacteriuria from 100% to 22.5%⁴. Similarly, bladder irrigation with 2% povidone-iodine prior to prostatectomy in patients with indwelling catheters was well tolerated and achieved urine sterilization in 75% of patients in another study⁵. While neither of these studies looked at reducing rates of CAUTI, we hypothesize that they could provide a benefit, given their effectiveness at decreasing bacteriuria in patients with indwelling catheters. Both studies

reported that a low concentration of 1 or 2% was well tolerated by patients. A study from the Netherlands evaluated use of pre-removal povidone-iodine bladder irrigation⁶. No reduction in bacteriuria was found in cultures at days 4 to 14 after removal, though there was a trend towards less bacteriuria in the first 3 days after removal. Additionally, more than half of the patients had only had catheters in place for 3 days or less prior to removal, and only 13.6% of patients had positive urine cultures prior to removal, which may have minimized the potential differences.

A single dose of povidone-iodine prior to catheter removal seems a novel and promising practice for several reasons. First, we suspect it will be helpful in reducing rates of NHSN defined CAUTI, as these are still diagnosed for 2 days after the catheter is removed. Results of a recent review revealed that 15-20% of diagnosed CAUTIs at Beaumont occurred during this window. Second, using multiple doses of povidone-iodine would be inadvisable, since we suspect bacteria over time would become resistant even to this antiseptic. Third, we suspect use of an antiseptic is preferable to an antibacterial for preventing further antimicrobial resistance development. Finally, use of this method, as opposed to the suggested use of systemic antibiotics at time of removal⁷, is potentially preferable from the downstream standpoint of less antimicrobial resistance and reduced risk of *Clostridium difficile* infection.

II. OBJECTIVE AND ENDPOINT

Objective:

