To evaluate the effectiveness of Betadine irrigation solution (2% povidone-iodine) instilled into the bladder immediately prior to indwelling catheter removal to decrease the risk of subsequent bacteriuria, leading to decreased rates of NHSN defined CAUTI.

Endpoint:

Presence or absence of NHSN defined CAUTI at 48-72 hours after indwelling urinary catheter removal, as assessed by urinalysis (UA), urine culture (UC), and UTI Symptom Assessment questionnaire (UTISA)⁸.

III. METHODOLOGY

A total of 110 men will be enrolled in this randomized trial, which will be conducted at Beaumont Hospital, Royal Oak. Eligible patients will be consented and randomized into 1 of 2

groups. Ideally, fifty-five men will be in each group. 120 men may need to be enrolled to achieve the desired number of patients completing the 48-72-hour post-catheter removal visit, which is the study endpoint.

Despite optimal "clean catch" collection techniques, it is often difficult to obtain a noncontaminated urine sample from females without performing sterile catheterization due to the chronically colonized vaginal flora. In order to minimize patient risks and difficulty with recruitment associated with additional catheterization, we have chosen to exclude females from this initial study. The male anatomy allows for adequate sample collection via "clean-catch" alone. By enrolling only males we hope to reduce the possibility of contamination in the cleancatch specimens collected at the 48-72 hour follow up visit⁹. Future studies would include females as well.

Study staff will review patient charts from all Beaumont Hospital, Royal Oak units (including rehabilitation units) in order to identify patients who may be eligible to participate. Appropriate patients will be approached, the study will be described to them in detail, and informed consent will be obtained. Eligibility criteria will be reviewed, including current antibiotic use, which is exclusionary. If the patient meets all of the inclusion criteria and none of the exclusion criteria, a urine sample will be obtained for UA and UC. All urine test results will be for research purposes only and not part of the patient's clinical chart/electronic medical record. All UA and UC results, collected for research, will be reviewed by one of the study investigators. If a patient develops symptoms at any point in the study, a UA and UC could be obtained at the care provider's discretion.

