- 4) Clinical signs or symptoms of urinary tract infection at the time of consent
- 5) Patients currently being treated for UTI
- 6) Patients currently taking any antibiotic medication, other than those listed in Appendix B
- 7) Patients already taking medications known to potentially irritate the bladder, such as, but not limited to, cyclophosphamide, ifosfamide, and other chemotherapeutic agents
- 8) Patients with history of bladder cancer, pelvic radiation or interstitial cystitis
- 9) Patients unable to comply with study requirements
- Any other condition which, per investigators' judgment, may increase patient risk and/or impede the reliability of study data

VII. DATA ANALYSIS

An infection rate of 25% is anticipated at day 2 post catheter removal for the SOC group. A difference has been shown of a 75% drop in infection rate using povidone-iodine bladder irrigation⁵. A power analysis using these estimates yields 55 patients needed in each arm to have 80% power at a 0.05 significance level to detect a difference of 25% versus 6.25%. We estimate at most a 10% dropout rate and plan to enroll 60 patients per arm to account for this.

Descriptive statistics will be provided for all data collected. Categorical variables will be reported as counts and percent frequencies. All continuous variables will be reported as means

+/- the standard deviation followed by the median, minimum to maximum or the median (25th, 75th percentiles) then minimum to maximum dependent on the normality of the data.

The endpoint of presence or absence of bacteriuria at 48-72 hours post catheter removal will be examined with a Fisher's exact tests, odds ratio and 95% confidence intervals. If any differences are found in what appear to be confounders for UA, a multivariate logistic regression analysis may be completed adjusting for these differences.

The categorical variables will be examined using Pearson's Chi-square tests where appropriate (expected frequency >5), otherwise Fisher's exact tests will be used. Continuous variables will be examined for normality. Normally distributed variables will be analyzed using t-tests. Non-normally distributed variables will be examined using non-parametric Kruskal-Wallis tests.

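### The declared endpoint is NHSN-defined CAUTI, but the analysis section tests bacteriuria and powers the trial on an undefined infection rate, so 80% power is not shown for CAUTI

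*Combined protocol and SAP*

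**What the plan says.** The documents use different labels for the outcome.

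- **Section II, Endpoint:** "Presence or absence of NHSN defined CAUTI at 48-72 hours after indwelling urinary catheter removal", assessed by urinalysis (UA), urine culture (UC) and the UTISA symptom questionnaire. No other endpoint is listed.
- **Section II, Objective:** irrigation is meant "to decrease the risk of subsequent bacteriuria, leading to decreased rates of NHSN defined CAUTI".
- **Section VII, sample size:** "An infection rate of 25% is anticipated at day 2 post catheter removal for the SOC group", then "A difference has been shown of a 75% drop in infection rate using povidone-iodine bladder irrigation", citing reference 5. From these come 25% versus 6.25%, 55 per arm, 80% power and a 0.05 significance level.
- **Section VII, test:** "The endpoint of presence or absence of bacteriuria at 48-72 hours post catheter removal" is to be examined with Fisher's exact test, an odds ratio and 95% confidence intervals.
- **Section VII, regression:** "If any differences are found in what appear to be confounders for UA", an adjusted logistic model may be fitted.
- **Section VII, other categorical variables:** Pearson "Chi-square tests where appropriate (expected frequency >5"), otherwise Fisher's exact test.

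Section I (Background and Rationale) reports that reference 5 "achieved urine sterilization in 75% of patients in another study". It adds that neither of the two prostatectomy studies examined CAUTI rates.

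**The concern.** Bacteriuria and CAUTI are not interchangeable in this protocol. The objective puts them in sequence, one leading to the other. The background says that most catheterised patients with bacteria in the urine are colonized rather than infected. The declared endpoint also draws on symptoms through UTISA, so a urine result alone cannot settle it.

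Two things are at stake. First, with two outcomes each called the endpoint, the primary result could be chosen after the data are seen, or a bacteriuria finding could be reported as a CAUTI finding. Second, the power statement is attached to no identified outcome, so a reader cannot tell whether the trial is adequately sized for what it says it will measure.

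**Working it through.** **1. Does the stated sample size reproduce?** Inputs from Section VII: p1 = 0.25; p2 = 0.25 × (1 − 0.75) = 0.0625; power 80%; significance level 0.05. Sidedness is not stated and is taken as two-sided. With the unpooled normal approximation,

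n = (z₀.₉₇₅ + z₀.₈₀)² × [p1(1 − p1) + p2(1 − p2)] / (p1 − p2)²

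= (1.960 + 0.842)² × (0.1875 + 0.0586) / 0.1875² ≈ 54.9, so 55 per arm.

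The plan's figure is reproduced. The arithmetic is sound for whichever outcome has those two rates.

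**2. Which outcome has those rates?**

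| Input | Label in Section VII | Support in the documents |
|---|---|---|
| 25% in the standard-of-care (SOC) arm | infection, day 2 | No definition or source. Day 2 fits CAUTI, which Section I says can still be diagnosed for 2 days after removal |
| 75% reduction | infection rate, reference 5 | Section I describes reference 5 as urine sterilization and says CAUTI was not examined |

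Section I also says that 15–20% of the hospital's diagnosed CAUTIs fell in the post-removal window. That is a share of diagnosed cases, not a rate among patients, so it cannot stand in for the 25%.

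**3. Power at 55 per arm under each reading.** Exact power is the sum of the two binomial probabilities over all tables that reject at two-sided 0.05.

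- *Bacteriuria, Fisher's exact test as planned:* 25% v 6.25% gives 0.716.
- *CAUTI, under the general categorical rule* (uncorrected Pearson chi-square if the smallest expected count exceeds 5, otherwise Fisher): 25% v 6.25% gives 0.798. The chi-square branch applies with probability 0.971.

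**4. Sensitivity for CAUTI.** The documents give no CAUTI rate at 48–72 hours. Every row below except the 25% v 6.25% row uses an assumed rate or reduction, under the same general rule at 55 per arm.

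| SOC rate | Reduction | Irrigation rate | Power |
|---|---|---|---|
| 30% | 75% | 7.5% | 0.886 |
| 25% | 75% | 6.25% | 0.798 |
| 20% | 75% | 5% | 0.660 |
| 15% | 75% | 3.75% | 0.454 |
| 10% | 75% | 2.5% | 0.210 |
| 5% | 75% | 1.25% | 0.030 |
| 25% | 50% | 12.5% | 0.396 |

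The table shows how strongly power depends on the two unstated inputs. It does not show that power for CAUTI is in fact low.

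**The case against.** The best defence is that Section VII is coherent if infection is loose wording for bacteriuria. Section I gives bacteriuria rising 3–10% per day, and Section VI (Eligibility Criteria) requires at least 5 catheter days. That implies about 14% to 41% by day 5 if compounded (1 − 0.97⁵ to 1 − 0.90⁵), or 15% to 50% if added, and 25% lies inside either range. The cited effect is on urine sterility, and the named test is for bacteriuria. Section I also says that the NHSN definition catches some patients who are only colonized, so the two outcomes overlap more than a simple contrast of infection with colonization suggests.

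This is a fair reading, but the protocol does not state that derivation. If it is right, the sample size and test concern bacteriuria while the declared endpoint is CAUTI. The contradiction with Section II remains, and power for CAUTI has no basis at all.

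Three narrower points stand:

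- The 72% arises from sizing by a normal approximation and then planning Fisher's test, and would exist even if both sections named bacteriuria. It is the figure to state if bacteriuria is chosen, not a measure of harm from the mismatch. It would be about 77% if all 60 planned per arm completed.
- No shortfall for CAUTI is demonstrated.
- The CAUTI case definition is brought in by citing the NHSN manual, so the gap is mainly how the study's UA, UC and UTISA results map onto it.

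**Conclusion.** The concern holds and needs correction. Section II and Section VII name different endpoints, and CAUTI has no named test. The documents support neither the 25% rate nor the 75% reduction for CAUTI. The 80% power is therefore not shown for the declared endpoint, although it is not shown to be wrong either.

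At 55 completers per arm, two-sided 0.05 and 25% v 6.25%, power is about 72% for bacteriuria with Fisher's test. For CAUTI it is about 80%, on condition that the general chi-square/Fisher rule is the intended test and both rates apply to CAUTI. Results at other rates rest on assumptions.

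**What to change.** Before outcome data are examined:

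1. Name one primary endpoint and use it in Section II, the sample-size paragraph, the primary test sentence and the regression sentence (in place of UA).
2. Make the other outcome a named secondary endpoint with an effect estimate and 95% confidence interval, and limit the primary conclusion to the chosen outcome.
3. State which outcome the 25% describes and why, and reconcile the Section I and Section VII descriptions of reference 5.
4. *If bacteriuria with Fisher's test is primary:* state what counts as bacteriuria at Visit 2, and restate power as about 72% at 55 per arm.
5. *If CAUTI is primary:* name its test and state how UA, UC and UTISA combine to define a case. Withdraw the 80% claim unless the 25% rate and 75% reduction are justified for CAUTI. If they are, the claim can stand under the existing chi-square/Fisher rule.

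The cost is protocol and SAP wording only, with no added patients. The price is a lower stated power, a withdrawn power claim or a narrower primary claim, depending on the choice.

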48-72 hours after catheter removal a urine sample will be obtained to repeat UA and UC. If enrolled patients are still inpatient at this time point, study staff will see the patient in the hospital and conduct the Visit 2 activities. If the patient has been discharged from the hospital, this visit will occur in the Urology Research office. While not ideal or preferred, if the patient is not available for an in-person visit, the questionnaire may be completed over the phone, or sent to the patient and returned by mail (returned by USPS, email, or fax). In addition to the UA and UC, the UTISA questionnaire will also be completed. The UTISA questionnaire is a validated tool which will be utilized to assess the "severity" and "bothersomeness" of the most frequently reported signs and symptoms of uncomplicated UTI⁸. The Beaumont laboratory will evaluate all collected specimens. If a patient develops symptoms suggestive of a UTI, then further testing may be performed at the discretion of their managing physician or one of the study investigators. Research staff will also contact patients by phone at 7 and 28 days after catheter removal. At that time the UTISA will be administered to assess urinary symptoms, including diagnosed UTIs since the time of catheter removal. The UTISA may be completed verbally over the phone or by mail (returned by USPS, mail, or fax). If the patient's responses indicate a possible UTI, the patient will be referred to their primary care provider and/or other health care provider for evaluation.

Patients requiring reinsertion of an indwelling catheter prior to study completion will be withdrawn from the study. Patients that do not comply with the study protocol may also be withdrawn from the study by the Principal Investigator (PI).

	Screening & Treatment Visit Inpatient Visit	Visit 2 48-72 Hours Clinic or Inpatient Visit	Visit 3 7 ± 3 days Phone Call	Visit 4 28 ± 3 days Phone Call
Informed Consent	Х			
Review Inclusion and Exclusion Criteria	Х			
Review of Current Antibiotic Medication Use	Х	Х	X	Х
Urine collection: UA & UC	Х	Х		
UTISA Questionnaire		Xa	Xb	Xb
Indwelling Catheter Removal	Х			
Betadine Bladder Irrigation	Xc			
Assess for Adverse Events	Х	Х	X	Х

SCHEDULE OF ACTIVITIES

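### The planned unadjusted Fisher test gives 71.6% power, not 80%, and leaves the baseline urine culture unused; the only adjusted analysis is optional, triggered by imbalance and names no covariates

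*Combined protocol and SAP*

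**What the plan says.** Section VII (Data Analysis) names the endpoint test: "The endpoint of presence or absence of bacteriuria at 48-72 hours post catheter removal will be examined with a Fisher's exact tests", with an odds ratio and 95% confidence interval. The same section says that the sample size calculation "yields 55 patients needed in each arm to have 80% power at a 0.05 significance level" for 25% versus 6.25%. For categorical variables in general it allows "Pearson's Chi-square tests where appropriate (expected frequency >5"), and Fisher's test otherwise.

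Adjustment appears once: "If any differences are found in what appear to be confounders for UA, a multivariate logistic regression analysis may be completed". The section does not say which variables are meant, how large a difference triggers the model, or which result leads if the two disagree.

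Section III (Methodology) has every eligible man give a baseline sample ("a urine sample will be obtained for UA and UC") and a second one later: "48-72 hours after catheter removal a urine sample will be obtained to repeat UA and UC". The baseline culture is not named as a stratum, covariate or subgroup anywhere. Section I (Background and Rationale) nevertheless notes of an earlier pre-removal irrigation trial that "only 13.6% of patients had positive urine cultures prior to removal, which may have minimized the potential differences".

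Section II gives a different endpoint: "Presence or absence of NHSN defined CAUTI at 48-72 hours after indwelling urinary catheter removal". The adjustment clause refers to a third quantity, urinalysis (UA).

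**The concern.** Three things come together in the endpoint analysis.

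- **Power.** Fisher's test runs well below its nominal level at this sample size, so the stated power may belong to a different test from the one planned.
- **Unused information.** A baseline measurement of the outcome variable is collected on every man and then left out of the comparison.
- **Pre-specification.** An optional model, started by observed differences in unnamed variables, leaves open which adjusted result will be reported.

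None of these biases the randomised comparison. At stake are a real chance of missing the effect that the trial is designed to find, and a loose end in reporting.

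**Working it through.** **Inputs.** From section VII: 25% in the standard-of-care (SOC) arm, 6.25% with Betadine (a 75% reduction), 55 per arm, alpha 0.05 (taken as two-sided), 60 per arm enrolled and at most 10% dropout. From section I: bacteriuria rises 3-10% per day. From section VI: catheter in place at least 5 days. The association between baseline culture and outcome is not given, so it is varied.

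**1. The plan's own figure.** Unpooled normal approximation:

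n = (1.96 + 0.8416)² × (0.25 × 0.75 + 0.0625 × 0.9375) / 0.1875² = 7.849 × 0.24609 / 0.03516 = 54.9, so 55 per arm. The stated number reproduces, but the formula is not based on Fisher's test.

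**2. Exact power and size** (full enumeration of two binomials):

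| Per arm | Fisher power | Pearson power |
|---|---|---|
| 54 (60 less 10%) | 70.5% | 79.6% |
| 55 | 71.6% | 80.4% |
| 60 (no dropout) | 76.6% | 83.3% |
| 64 | 80.1% | 85.8% |

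At 55 per arm and a common rate of 25%, type I error is 3.0% for Fisher and 5.0% for Pearson. Over common rates of 1-50% the maxima are 3.2% and 5.3%. Fisher's test needs 64 evaluable men per arm for 80% power.

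**3. The plan's own rule for Pearson.** Expected events are 55 × (0.25 + 0.0625) = 17.2, or 8.6 per arm, which is above the threshold of 5.

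**4. CMH test stratified by baseline culture, no continuity correction** (simulation, 55 per arm, 200,000 trials per cell). SOC stratum risks average 25%, and risk falls by 75% in both strata. Baseline positivity of 15-50% is 5 days at 3-10% per day. The covariate's own effect is CMH minus Pearson:

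| Baseline-outcome odds ratio | Change in power, points (15-50% positive) |
|---|---|
| 1 | -0.5 to -0.4 |
| 3 | +0.1 to +0.8 |
| 5 | +1.1 to +1.9 |
| 10 | +3.1 to +4.6 |
| 30 | +5.4 to +8.9 |

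At odds ratio 1, CMH power is about 80%. Its type I error is 4.9-5.0%. Five days is only a minimum; at 70-90% baseline-positive the change is -0.5 to +2.5 points over all these odds ratios. With a continuity correction, power falls to 71-74% at odds ratios 1 to 5, which gives up most of the gain over Fisher.

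**5. Estimate.** The 95% interval for the Mantel-Haenszel risk difference (Sato variance) covers the true 18.75 points in 94.3-95.6% of trials. Its half-width is 13.0 points at odds ratio 1 and 12.7-12.8 at 5, against 12.9 unadjusted. A constant 75% reduction does not give a common odds ratio: at baseline odds ratio 5, the treatment odds ratios (SOC to Betadine) are 5.9-7.7 in culture-positive men and 4.4-4.7 in culture-negative men.

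**6. Choice of result under the null** (simulation):

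| Freedom left to the analyst | False positives |
|---|---|
| Fisher, or baseline-culture regression only after a 10-point imbalance | 3.2-3.7% |
| Free choice of Fisher or a baseline-culture-adjusted result | about 5-6.5% |
| Four assumed covariates, 10-point trigger respected | 4.3-5.5% |
| Best of 15 models, trigger ignored | 8-11% |

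The 10-point trigger and the four covariates are assumptions. The last row is a worst case.

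**The case against.** The strongest reply is that the gap of 8 to 9 points is a mismatch between the sample size formula and the test. Naming Pearson's test or recalculating the sample size would close it without any covariate. That is true, and most of the gain does come from leaving Fisher's test. The covariate's own gain is at most about 2 points up to odds ratio 5; larger gains need an association that the documents do not support or exclude. The remark in section I about the earlier trial concerns its population. It shows that the authors think pre-removal culture matters, not that it predicts outcome among these men.

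It is also fair that Fisher's test guarantees its level while Pearson's slightly exceeds it at some rates (maximum 5.3%), that the regression clause could in principle take in the baseline culture, and that the false-positive cost is small if a trigger is respected.

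A further point is that no test recovers 80% if only baseline-positive men benefit. At 15-50% positive and odds ratios 3 to 10, power is then 9-66% for CMH and 10-63% for Pearson, and the covariate changes it by -0.8 to +2.4 points. But the overall treated rate is then no longer 6.25%, so that scenario lies outside the plan's own design assumption.

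These points limit the size of the concern. They do not remove it: the planned test does not deliver the stated power, and even zero dropout gives only 76.6%. Stratifying costs about half a point if the culture is uninformative.

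**Conclusion.** The concern holds and should be acted on. Under the plan's own 25% versus 6.25%, the planned test has 71.6% power at 55 per arm, 8.4 points below the stated 80%. An uncorrected CMH test on the baseline culture restores about 80% with type I error near 5%. Any gain beyond that depends on an unknown association. The exact Fisher and Pearson figures rest only on the design rates and a two-sided 5% level; the CMH figures also rest on the assumed baseline prevalence and on the same 75% reduction in both strata. Confidence is medium, because the strength of the covariate is unknown and the choice of test depends on which endpoint is kept.

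**What to change.** 1. Reconcile the endpoint first: section II names NHSN-defined CAUTI and section VII tests bacteriuria. If bacteriuria is meant, state the culture threshold and apply it at both time points.
2. Pre-specify a CMH test **without continuity correction**, stratified by baseline culture (positive or negative, from the sample taken before irrigation), done whatever imbalance is seen.
3. Report the Mantel-Haenszel stratified risk difference with 95% confidence interval (Sato variance) as the main estimate and a common odds ratio as secondary. Give counts and a risk difference for each stratum.
4. Keep the unadjusted Fisher test as a sensitivity analysis.
5. Delete the imbalance trigger. Limit any supportive regression to one or two covariates named in advance, since only about 17 events are expected.
6. Keep men without a valid baseline culture in the analysis as a third stratum. The figures above did not test this, so check it if there are more than a few such men.
7. If CAUTI is kept as the tested endpoint, recheck the expected number of events and use an exact stratified test if they are few.

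The cost is SAP wording, settled before outcomes are compared by arm. The culture is already collected, so no extra men, visits or tests are needed.
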